6.5.4. Ordinal Clinical Outcome at D5V or D11V

The OCO at D5V is defined as follows:

If the subject died at any point of study participation, then OCO at D5V will be 8.

Else if the subject has missing clinical improvement at D5V then OCO at D5V will be missing.

Else if the subject did not have clinical improvement at D5V and was hospitalized then OCO at D5V will be 7.

Else if the subject did not have clinical improvement at D5V with ED, outpatient clinic, or urgent care visit but was not hospitalized then OCO at D5V will be 6.

Else if the subject did not have clinical improvement at D5V and did not have any medically attended events then OCO at D5V will be 5.

Else if the subject has missing most severe solicited event at D5V as defined in Section 6.5.3 then OCO at D5V will be missing.

Else if the subject had clinical improvement at D5V and a most severe solicited event of grade 3 at D5V then OCO at D5V will be 4.

Else if the subject had clinical improvement at D5V and a most severe solicited event of grade 2 at D5V then OCO at D5V will be 3.

Else if the subject had clinical improvement at D5V and a most severe solicited event of grade 1 at D5V then OCO at D5V will be 2.

Else if the subject had clinical improvement at D5V and did not experience any solicited event through D5V (i.e.; the most severe solicited event at D5V is of grade 0) then OCO at D5V will be 1.

The OCO at D11V is defined in a similar manner by replacing D5V by D11V in the above algorithm.

Note that in some cases OCO can be defined even if some components are missing. For instance, if a subject had record of receipt of study product and did not have clinical improvement at D5V, OCO at D5V would still be defined even if most severe solicited event at D5V was missing since the above algorithm doesn't take solicited events severity into account for OCO levels 5, 6, 7, and 8.

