6.5.3. Most Severe Solicited Event for DOOR

If a subject had severity grades (0 to 3) recorded for every solicited event (abdominal pain, vomiting, diarrhea, allergic reaction, and candidiasis) from Study day 1 to D5V Study day, inclusive, then the most severe solicited event at D5V, a component of DOOR, will be the maximum severity grade taken across all solicited events from Study Day 1 to D5V Study Day.

If a subject had any solicited event of severity grade 3 from Day 1 to D5V Study Day, then the most severe solicited event at D5V will be grade 3, regardless of the presence of missing data during that period. Otherwise, if the subject has missing data for the severity grade of any solicited event from Day 1 to D5V study day, then most severe solicited event at D5V will be missing.

If a subject had severity grades (0 to 3) recorded for every solicited event (abdominal pain, vomiting, diarrhea, allergic reaction, and candidiasis) from study day 1 to study day 11, inclusive, then the most severe solicited event at D11V, a component of DOOR at D11V, will be the maximum severity grade taken across all solicited events from study day 1 to study day 11.

If a subject had any solicited event of severity grade 3 from Day 1 to study day 11 study day, then the most severe solicited event at study day 11 will be grade 3, regardless of the presence of missing data during that period. Otherwise, if a subject has missing data for the severity grade of any solicited event from Day 1 to study day 11 study day, then most severe solicited event at D11V will be missing.

A similar approach as described above will be used to determine the most severe solicited event at D28V by considering all solicited events reported post dose 1.

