This F-distribution is used to compute a p-value (one-sided probability) from the overall test statistic W . The null hypothesis will be rejected if $p < 0.05$.

A corresponding 95% CI for U will be computed using the overall test statistic W through the inversion of the F-test. Dividing the bounds of this CI by $n_1 n_2$ will yield the bounds for the 95% CI of $\text{Pr}(\text{Higher DOOR in placebo}) + 0.5 \text{Pr}(\text{Equal DOOR in azithromycin})$. Thus, the CI for DOOR probability is given by:

$$95\% \text{ CI: } \left(\frac{\bar{Q} - \sqrt{T \times F_{0.95,1,\nu}}}{n_1 n_2}, \frac{\bar{Q} + \sqrt{T \times F_{0.95,1,\nu}}}{n_1 n_2} \right)$$

A point estimate of the DOOR probability will be obtained by dividing \bar{Q} by $n_1 n_2$. Results will be shown in [Table 37](#) for ITT population.

Analysis of DOOR will be repeated for the ATP-5 analysis population and using the same multiple imputation model as ITT analysis. Results of this analysis will be reported in [Table 38](#).

Additional analyses of DOOR at D5V will be performed using only subjects in the ATP-5 population with complete data. These analyses will test the null hypotheses described above using the Mann-Whitney U Test, estimate $\Pr(\text{Higher DOOR in placebo}) + 0.5 \Pr(\text{Equal DOOR})$ using U divided by the number of pairwise comparisons, and will compute confidence intervals by (1) inverting the Mann-Whitney U Test and (2) using a non-parametric bootstrap.

Confidence intervals from inverting the Mann-Whitney U Test will be given by:

$$\left(\frac{U}{n_1 n_2} - 1.96 \times \sqrt{\frac{\text{Var}(U)}{(n_1 n_2)^2}}, \frac{U}{n_1 n_2} + 1.96 \times \sqrt{\frac{\text{Var}(U)}{(n_1 n_2)^2}} \right)$$

Correcting for ties, the formula for the variance of U is:

$$\text{Var}(U) = \frac{n_1 n_2}{12} \left[(n_1 + n_2 + 1) - \frac{1}{(n_1 + n_2)(n_1 + n_2 + 1)} \sum_{c=1}^D (M_c^3 - M_c) \right]$$

where M_c is the number of tied ranks for the c^{th} value DOOR in the dataset and D is the number of distinct values of DOOR in the dataset.

Confidence intervals for the DOOR probability using a non-parametric bootstrap:

$$\left(\frac{U_{0.025}}{n_1 n_2}, \frac{U_{0.975}}{n_1 n_2} \right)$$

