8.3.8. New occurrence of Fever at D11V Using ATP-11 Analysis Population

Using ATP-11, a forest plot of 95% CIs for the risk difference of fever in the 24 hours preceding or at D11V will be provided in [Figure 15](#). Results of fever at D11V will also be reported in [Table 45](#). Tests for differences in proportions between treatment arms will be given by Fisher's exact tests. The Miettinen–Nurminen method will be used to compute all 95% CIs for risk differences.

8.3.9. Bivariate Analysis of DOOR and Number of Days of Antibiotics Use at D5V and D11V

In addition to the DOOR analyses described in Section 8.2.8, a two-dimensional analysis of the DOOR probability and difference in the mean duration of antibiotic use in the two treatment groups will also be performed at D5V. Only subjects with non-missing DOOR and number of days on antibiotics will be included in these analyses. The horizontal axis is the DOOR probability (probability of a more desirable outcome when assigned to placebo vs. azithromycin) based on the ordinal DOOR outcome ignoring the duration of antibiotic use. The vertical axis is the difference in the means of the observed (outcome not assignment) duration of antibiotic use (placebo minus azithromycin). A result in the lower right quadrant represents more desirable results for placebo, while a result in the upper left represents more desirable for azithromycin. The other two quadrants represent tradeoffs for clinical outcomes and antibiotic use.

1000 bootstrap samples will be generated by resampling with replacement from the empirical distribution of DOOR and number of days of antibiotics use at D5V. The DOOR probability and mean difference in the number of days of antibiotics use will be estimated using the bootstrap samples and plotted as a scatter plot. A 95% joint region of DOOR probability and duration for antibiotic will be constructed first using a parametric method and repeated using a nonparametric method. The parametric method will estimate the confidence region using the ellipse method from the CAR R package which uses a bivariate normal distribution. The nonparametric will use distribution-free approach implemented in the distfree.cr R package proposed by Hu and Yang (2013) in [12]. Marginal distributions of DOOR probability and difference in duration of antibiotics will be provided. To confirm the robustness of these results, these plots will be regenerated using 2000

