Subjects with non-missing DOOR– n (%)	x (x)
Pr(Higher DOOR in Placebo Arm) ^a (95% CI) ^b	x.xx (x.xx, x.xx)
P-value ^c	x.xxx

Note: DOOR was calculated based on subjects with non-missing OCO at atleast one of the timepoints. Missing values were ignored when calculating average OCO.
 
^aProbability of Higher DOOR in Placebo Arm + 0.5 Probability of Equal DOOR. CI obtained through inversion of the F-test used to compute the p-value.
 
^bObtained through using inversion of the Mann-Whitney U test with a normal approximation and assuming the null hypothesis distribution variance provided in Section 8.2.8 correcting for ties.
 
^cP-value obtained by Mann-Whitney U Test. P-value boundary of 0.05 is used to conclude statistical significance.
	

Table 56: Risk of Mild, Moderate, or Severe Solicited Events from Study Day 1 to D5V - ATP-5 Analysis Population

Symptom	Azithromycin (N=X)		Placebo (N=X)		Risk Difference (95% CI) ^b	P-Value ^c
	n (%)	95% CI ^a	n (%)	95% CI ^a		
Any Symptom	x (x)	(x, x)	x (x)	(x, x)	x.x (x.x, x.x)	x.xxx
Abdominal Pain	x (x)	(x, x)	x (x)	(x, x)	x.x (x.x, x.x)	x.xxx
Vomiting	x (x)	(x, x)	x (x)	(x, x)	x.x (x.x, x.x)	x.xxx
Diarrhea	x (x)	(x, x)	x (x)	(x, x)	x.x (x.x, x.x)	x.xxx
Allergic Reaction	x (x)	(x, x)	x (x)	(x, x)	x.x (x.x, x.x)	x.xxx
Candidiasis	x (x)	(x, x)	x (x)	(x, x)	x.x (x.x, x.x)	x.xxx

N = Number of subjects in the ATP-5 analysis population and the respective treatment group with complete records from study Day 1 to D5V.
^a95% CI for proportions calculated using the Wilson method.
^b95% CI for the difference in proportions, placebo relative to azithromycin, calculated using the Miettinen–Nurminen method.
^cP-values obtained by Fisher’s Exact Test.

Table 57: Risk of Moderate or Severe Solicited Events from Study Day 1 to D5V - ATP-5 Analysis Population

Symptom	Azithromycin (N=X)		Placebo (N=X)		Risk Difference (95% CI) ^b	P-Value ^c
	n (%)	95% CI ^a	n (%)	95% CI ^a		
Any Symptom	x (x)	(x, x)	x (x)	(x, x)	x.x (x.x, x.x)	x.xxx
Abdominal Pain	x (x)	(x, x)	x (x)	(x, x)	x.x (x.x, x.x)	x.xxx
Vomiting	x (x)	(x, x)	x (x)	(x, x)	x.x (x.x, x.x)	x.xxx
Diarrhea	x (x)	(x, x)	x (x)	(x, x)	x.x (x.x, x.x)	x.xxx
Allergic Reaction	x (x)	(x, x)	x (x)	(x, x)	x.x (x.x, x.x)	x.xxx
Candidiasis	x (x)	(x, x)	x (x)	(x, x)	x.x (x.x, x.x)	x.xxx

N = Number of subjects in the ATP-5 analysis population and the respective treatment group with complete records from Study Day 1 to D5V.

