Figure 13: Forest Plot of Risk Difference, Placebo Group Relative to Azithromycin, of Deterioration in the Symptom or Sign on Day 11 - ATP-11 Population

Figure 14: Forest Plot of Risk Difference, Placebo Group Relative to Azithromycin, of New Occurrence of Vital Sign Abnormality on Day 5 - ATP-5 Population

[figure not shown]

Figure 15: Forest Plot of Risk Difference, Placebo Group Relative to Azithromycin, of Fever on Day 11 - ATP-11 Population

[figure not shown]

Figure 16: Distribution of Ordinal Clinical Outcome Used for DOOR by Treatment Group and Timepoint

[figure not shown]
[figure not shown]

Figure 17: Cumulative Distribution Function for Ordinal Clinical Outcome Used for DOOR by Treatment Group at D5V - ITT Population

[Implementation note: Subjects with missing OCO will be excluded from this plot. 95% confidence bands will be added to the plot. Pseudocode: <https://communities.sas.com/t5/SAS-Programming/Add-upper-and-lower-confidence-limit-CDF-curves/m-p/316651#M69236>]

Figures with similar format:

Figure 18: Cumulative Distribution Function for Ordinal Clinical Outcome Used for DOOR by Treatment Group at D5V - ATP-5 Population

Figure 19: Cumulative Distribution Function for Ordinal Clinical Outcome Used for DOOR by Treatment Group at D11V - ITT Population

Figure 20: Cumulative Distribution Function for Ordinal Clinical Outcome Used for DOOR by Treatment Group at D11V - ATP-11 Population

Figure 21: Bivariate Analysis of DOOR at D5V - ITT Analysis Population with Complete Data at D5V

[Implementation Note: This figure will have 4 panels; the rows will represent the number of bootstrap samples (1000, 2000) and the columns will represent the parametric vs non-parametric approach. The ellipse function from the CAR package will be used to estimate the confidence regions using the parametric method and the distfree.cr R package for the distribution free approach will be used to estimating confidence regions. Marginal distributions of difference in duration of antibiotics use and DOOR probability will be added to the plot. This figure will be generated only if the variability in the number of days of antibiotic use justifies making such a figure.]

[figure not shown]

Figure with similar format:

Figure 22: Bivariate Analysis of DOOR at D11V - ITT Analysis Population with Complete Data at D11V

Figure 23: Distribution of Daily Ordinal Clinical Outcomes from Study Day 1 to Study Day 11 by Treatment Group and Timepoint - ITT Population

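### A blank solicited-event grade makes the ordinal outcome missing only for improved subjects without a grade 3, so complete-case OCO and DOOR displays over-represent failures

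*SAP*

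**What the plan says.** SAP 6.5.4 works down a list. Death gives OCO 8, and unknown clinical improvement gives a missing OCO. A subject without improvement gets 7, 6 or 5, according to hospitalization and other medically attended events. Solicited events are read only after that: "Else if the subject has missing most severe solicited event at D5V as defined in Section 6.5.3 then OCO at D5V will be missing". The section notes that failures stay defined because the algorithm does not "take solicited events severity into account for OCO levels 5, 6, 7, and 8".

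SAP 6.5.3 defines when the solicited-event component is missing. It is missing "if the subject has missing data for the severity grade of any solicited event from Day 1 to D5V study day", even if a grade 1 or 2 was recorded. The one exception is a recorded grade 3: "then the most severe solicited event at D5V will be grade 3, regardless of the presence of missing data during that period". The D11V rule has the same form over Days 1 to 11, and D28V follows a similar approach. Under SAP 6.5.6 a missing OCO makes DOOR missing.

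Several outputs then use only subjects with a defined OCO or DOOR:

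- SAP 8.2.8 and 8.3.3 (Table 48): "Additional analyses of DOOR at D5V will be performed using only subjects in the ATP-5 population with complete data", repeated for ATP-11. SAP 6.5 presents the ATP analyses with and without imputation as a test of the imputation model.
- SAP 8.3.9 (Figures 21 and 22): "Only subjects with non-missing DOOR and number of days on antibiotics will be included in these analyses".
- Figures 17 to 20 (implementation note under Figure 17): "Subjects with missing OCO will be excluded from this plot".
- SAP 8.3.10.3 and 8.3.10.4 (Tables 54 and 55): missing OCOs are skipped when a subject's average is formed.

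**The concern.** Whether the OCO is missing depends on the outcome by construction. In ATP-5, clinical improvement is known for everyone but a missing DOOR is allowed (SAP 6.3.2), so every missing OCO there belongs to an improved subject. The rule also discards known information: such a subject is certainly in OCO 1 to 4 and so ranks above every failure.

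Two things are at stake. The complete-case displays show a worse outcome distribution than the data support. And Table 48, meant as a check on the imputation, can differ from Tables 38 and 47 because of this selection, with nothing wrong in the imputation model.

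**Working it through.** **The rule with one blank cell.** Applying SAP 6.5.3 and 6.5.4 literally:

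| Subject | Complete diary | One blank |
|---|---|---|
| Improved, maximum grade 0, 1 or 2 | OCO 1, 2 or 3 | missing |
| Improved, grade 3 recorded | OCO 4 | OCO 4 |
| Failure without a medically attended event, any grade | OCO 5 | OCO 5 |

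So OCO 1 to 3 lose subjects, while OCO 4 and the failures do not.

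**Inputs from the plan.** Improvement rate 57.6%, hence 42.4% failures, and 560 subjects in ATP-5 (SAP 5). There are five solicited events per day, and D5V falls on Day 5 to 8 (SAP 3.3.1). That gives 25 to 40 cells at D5V and 55 to Day 11. The plan states no figure for missing OCO, so there is none to reproduce.

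**Assumed inputs.** b is the share of improved subjects with at least one blank; g is the share of improved subjects with a recorded grade 3. Neither is in the documents.

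**Failure share among retained ATP-5 subjects** = 0.424 / (0.424 + 0.576 × (1 − b(1 − g))). Improved subjects dropped = 560 × 0.576 × b(1 − g).

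| b | Share, g = 0 | Share, g = 5% | Dropped, g = 0 |
|---|---|---|---|
| 5% | 43.7% | 43.6% | 16 |
| 10% | 45.0% | 44.9% | 32 |
| 20% | 47.9% | 47.6% | 65 |
| 30% | 51.3% | 50.7% | 97 |

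**What gives such a b.** With independent cells, b = 1 − (1 − q)^k. At q = 0.5% per cell this is about 12% (25 cells), 18% (40 cells) and 24% (55 cells). With whole-day gaps at 2% per day it is 1 − 0.98^5 = 9.6%, 1 − 0.98^8 = 14.9% and 1 − 0.98^11 = 19.9%.

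**Arm comparison.** Assume identical true outcomes, a grade mix of 70/20/8/2% (grades 0 to 3) among improved subjects, and failures split 90/10 over OCO 5 and 6. For the tie-broken column, every azithromycin subject has more antibiotic days than every placebo subject, so each OCO tie goes to placebo. Values are the DOOR probability in favor of placebo.

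| Gaps, azithromycin / placebo | OCO only | With antibiotic-day tie-breaker |
|---|---|---|
| 0 / 0 | 0.500 | 0.663 |
| 10% / 10% | 0.500 | 0.664 |
| 10% / 25% | 0.477 | 0.642 |
| 25% / 10% | 0.523 | 0.688 |

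The first column corresponds to the horizontal axis of Figures 21 and 22, the second to Table 48.

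**Tables 54 and 55.** In Table 54 a blank removes only that day's OCO. In Table 55 one blank in the first five days falls inside the D5V and D11V windows and, read the same way, the D28V window. A subject without a grade 3 who improved at all three visits then has no OCO at all. One who failed at D5V with no medically attended event and improved later is averaged on the single value 5.

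**The case against.** The strongest reply is that little of importance rests on these displays, and most of it stands. The primary endpoint does not use the OCO. The main DOOR results (Tables 37, 38, 46 and 47) are multiply imputed, with observed clinical improvement and daily solicited severity in the model (SAP 8.4.2). Table 53 counts clinical improvements and does not use the OCO, so it would be wrong to infer that every complete-case DOOR result is affected. Tables 49 to 51 carry a Missing row with N as the population size; on that layout they understate OCO 1 to 3 and do not inflate failures. SAP 6.1 bases percentages on the non-missing sample, so that denominator needs stating.

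A reader might also infer that the rule produces false treatment effects. The documents do not support that. Equal gap rates leave the OCO-only probability at 0.500, the trial is double-blind, and nothing suggests different gap rates by arm. Nor is there a planned test of single-visit OCO alone on complete cases. Table 48 tests DOOR with the antibiotic-day tie-breaker. ATP-5 requires five doses, so under the assumptions above its value is about 0.66 without any gaps. With 280 per arm the null standard error, ignoring ties, is √(561 / (12 × 280 × 280)) = 0.024. The test therefore rejects almost always, with or without gaps; only the estimate moves. Figures 21 and 22 plan no such test and are produced only if antibiotic use varies enough.

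Gaps may also be rarer than assumed. Memory aids are reviewed with the subject for missing data (protocol 8.1). D5V symptoms come from the same form on the visit date, so a whole-day gap is unlikely on that day in ATP-5; at 2% per day, four days give 1 − 0.98^4 = 7.8% in place of 9.6%. This lowers b but leaves the rule as it is.

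**Conclusion.** The point holds for complete-case results built on the OCO: Table 48, Figures 17 to 22, Table 55 and, to a lesser extent, Table 54. They over-represent failures, and slightly OCO 4, even if blanks are completely random. With an assumed 5% to 20% of improved subjects having a blank, the ATP-5 failure share reads about 44% to 48% against 42.4%. Bias between arms needs unequal gap rates. At an assumed 10% versus 25%, the OCO-only probability moves from 0.50 to about 0.48 or 0.52, and the tie-broken value from about 0.66 to about 0.64 or 0.69. These sizes rest on assumed gap rates and an assumed grade mix. This is a flaw in a robustness check and in exploratory or descriptive displays; it does not threaten the trial's main conclusion.

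**What to change.** Keep the multiple imputation for the main DOOR analyses. In the complete-case OCO and DOOR displays, retain improved subjects with blanks in one of two ways:

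- impute only the solicited-event grade, within improved subjects, so that the OCO stays in 1 to 4 and no lower than the recorded maximum implies; or
- report two bounds, with blanks as grade 0 and blanks as grade 3.

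Either way improved subjects stay in OCO 1 to 4, so the ATP-5 failure share stays at 42.4% in the example above. Taking the maximum recorded grade as the only derivation is not advised: it treats blanks as grade 0 and would displace the imputation.

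State the percentage denominator for Tables 49 to 51. Tables 56 to 61 restrict the denominator to complete records (Table 56: "N = Number of subjects in the ATP-5 analysis population and the respective treatment group with complete records from study Day 1 to D5V"). If they are changed, treat subjects with and without events alike, for example with the same two bounds. Restoring only subjects with a recorded event would inflate event rates.

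The cost is SAP wording, some derivation code, and, if bounds are used, a range in place of a single value. No new data are needed.

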6.5.5. Number of Days of Antibiotic Use at D5V, D11V, or D28V

Analysis involving comparisons of the number of days of antibiotic use will consider all antibiotic use from Day 1 onwards including study antibiotics and non-study antibiotics for systemic use. The number of days of antibiotic use is defined as the actual number of days of antibiotic use (any amount of study product that is not placebo, or any amount of other systemic antibiotic) from Day 1 to D5V study day inclusive for D5V, from Day 1 to D11V study day inclusive for D11V, and from Day 1 through D28V study day inclusive for D28V. For subjects that received placebo as study product, it is counted as the number of days of systemic antibiotic as determined solely from the concomitant medication form. For subjects that receive actual antibiotic as study product, it is counted as the number of days that the subject received any amount of either study product or a non-study systemic antibiotic, as determined from the concomitant medication form. Note that missed doses of study product do not necessarily lower the number of days of antibiotic use as long as a separate dose of antibiotic (study product antibiotic or concomitant medication antibiotic) was received on that day. The number of days of antibiotic use is missing (at D5V, D11V, and D28V) if the product administration record was not completed for the subject and the subject did not have non-study systemic antibiotic use during the study period recorded as a concomitant medication.

The number of days of antibiotic use at the time of analysis will be determined from the product administration records and concomitant medication records only. Data management activities and site queries (outside the scope of this document) prior to data lock will ensure concomitant medication records are as complete as possible and consistent with other records (i.e., AEs and medically attended visit records in the clinical database). The number of days of antibiotic use for a concomitant medication will be calculated as the medication end date minus the medication start date plus one day. Days will not be double counted if multiple systemic antibiotics (including antibiotic as study product) are taken on the same day. Systemic antibiotic use will not be counted for days that fall outside of the range being considered for each subject (Days 1 to D5V study day, or Day 1 to D11V study day, or Day 1 to D28V study day).

If there is a start date but not an end date for a concomitant medication in the clinical database, then the end date for analysis will be imputed as follows. If the subject completed the study, then the end date for analysis will be reported as the protocol completion date. If the subject terminated early from the protocol and there is at least one other record for the same antibiotic in the concomitant medications records with start and end date known (record may belong to any subject), the end date of treatment for that antibiotic will be imputed by adding the mean observed number of days of treatment rounded up to the nearest integer for that antibiotic (minus 1). If no such records exist for the antibiotic and the subject terminated early, the end date of treatment for that antibiotic will be imputed by adding to the start date the mean observed number of days of treatment rounded up to the nearest integer for all systemic antibiotics in the concomitant medication records (minus 1).

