ATP	Any Reason							
	Subject was excluded from ITT analysis population							
	Subject had major protocol deviation related to I/E criteria							
	-Deviation Type 1							
	-Deviation Type 2							
	Did not consume 5 doses of study product by D5V							
	First dose of study product not taken within 24 hours of randomization							
	Dosing not resumed within 24 h of a missed dose							
	ATP-5	Any Reason						
		Subject was excluded from ATP analysis population						
Subject did not complete D5V								
D5V occurred out of the protocol defined window of Day 5 + 3 days								
D5V was not completed in person								
Data collected is insufficient to define clinical improvement at D5V								
ATP-11	Any Reason							
	Subject was excluded from ATP analysis population							
	Subject did not complete D11V							
	D11V occurred out of the protocol defined window of Day 11 + 3 days							
ATP-28	Any Reason							
	Subject was excluded from ATP analysis population							
	Subject did not complete D28V							
	D28V occurred out of the protocol defined window of Day 28 ± 2 days							
	Data collected is insufficient to define clinical improvement at D28V							

N = Number of subjects enrolled in the PCT ≤ 0.25 ng/mL cohort.

Table 10: Dates of PCT Screening by Site and Treatment Group - ITT Population

Site	Treatment Group	December 2017 - November 2018	December 2018 - November 2019	December 2019 – March 2020
Any	Any	x	x	x
Any Site	Azithromycin	x	x	x
	Placebo	x	x	x
Atlanta VA Medical Center	Azithromycin	x	x	x
	Placebo	x	x	x
Duke University	Azithromycin	x	x	x
	Placebo	x	x	x
Duke Regional Hospital	Azithromycin	x	x	x
	Placebo	x	x	x
Durham VA Medical Center	Azithromycin	x	x	x
	Placebo	x	x	x
Hope Clinic of the Emory Vaccine Center	Azithromycin	x	x	x
	Placebo	x	x	x
Houston VA Medical Center	Azithromycin	x	x	x
	Placebo	x	x	x

Table 11: Treatment Compliance by Treatment Group - ITT Population

[Implementation Note: Subjects who did not submit a product administration record (PAR) form, but who noted discontinuing from the study/treatment due to 'enrolled but treatment not administered' will be counted as having 0 doses. For subjects who did not submit a PAR form discontinued due to other reasons, they will be counted as having unknown number of doses.]

Treatment Compliance	Number of Doses Received	Azithromycin (N=X)		Placebo (N=X)		All Subjects (N=X)	
		x	x.X	x	x.X	n	%
Received all scheduled doses	5 Doses	x	x.X	x	x.X	x	x.X
Received <5 doses	4 Doses	x	x.X	x	x.X	x	x.X

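### With no product administration record, SAP 6.5.5 turns some true zero antibiotic-day counts into missing and gives some azithromycin subjects a count without study-drug days; in completers, an antibiotic with no stop date runs to study completion

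*SAP*

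**What the plan says.** SAP 6.5.5 builds the count from two sources; it "will be determined from the product administration records and concomitant medication records only". For placebo recipients "it is counted as the number of days of systemic antibiotic as determined solely from the concomitant medication form". For azithromycin recipients "it is counted as the number of days that the subject received any amount of either study product or a non-study systemic antibiotic". The missing rule begins: "The number of days of antibiotic use is missing (at D5V, D11V, and D28V) if the product administration record was not completed". The condition has a second part, so in full the count is missing "if the product administration record was not completed for the subject and the subject did not have non-study systemic antibiotic use" recorded during the study period. That missing rule is one rule for all three visits and makes no exception by arm or for subjects never dosed.

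The implementation note to Table 11 (SAP Appendix 1) takes a different line on never-dosed subjects. With no PAR, a subject who discontinued because treatment was not administered "will be counted as having 0 doses"; other subjects with no PAR have an unknown number of doses.

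For an antibiotic with a start date but no end date, SAP 6.5.5 says: "If the subject completed the study, then the end date for analysis will be reported as the protocol completion date". Early terminators instead get the mean observed duration for that antibiotic or, failing that, for all systemic antibiotics. All counts are cut at the visit day: "Systemic antibiotic use will not be counted for days that fall outside of the range being considered for each subject".

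**The concern.** Antibiotic days are the only tie-breaker in DOOR (SAP 6.5.6), they are a secondary outcome in their own right (SAP 3.2.2, item 1), and they form one axis of the bivariate analysis (SAP 8.3.9). A missing count makes DOOR missing and sends the subject to multiple imputation.

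In the placebo arm the missingness depends on the value itself. Among followed placebo subjects with no PAR, those with antibiotic days keep their count and only those with zero lose it. SAP 8.4.2 assumes missing at random for DOOR, but its imputation variables include neither antibiotic days nor PAR status.

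In the azithromycin arm the opposite happens: an unknown exposure becomes a definite, low number. The stop-date rule treats two subjects with the same incomplete record differently according to whether they finished the study.

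**Working it through.** **1. The plan's own example.** SAP 6.5.6 scores each subject as ordinal clinical outcome (OCO) + days/100 and ranks with mid-ranks. The four subjects have (OCO, days) of A (1, 5), B (1, 0), C (2, 0), D (1, 5). The scores are 1.05, 1.00, 2.00, 1.05 and the DOOR ranks 2.5, 1, 4, 2.5. This reproduces the SAP.

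**2. The missing rule, applied literally.** Study-drug days are counted only from a PAR, since the SAP names no other source. The visits are taken on Days 5, 11 and 28. The antibiotic dates are assumptions for illustration.

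| Subject | SAP 6.5.5, Day 5 / 11 / 28 | What the records support |
|---|---|---|
| Placebo, PAR, no antibiotic | 0 / 0 / 0 | 0 / 0 / 0 |
| Placebo, no PAR, followed, no antibiotic | missing | 0 / 0 / 0 |
| Placebo, no PAR, antibiotic Days 4–10 | 2 / 7 / 7 | 2 / 7 / 7 |
| Never dosed, no PAR, followed, no antibiotic | missing | 0 / 0 / 0 |
| Azithromycin, no PAR, no other antibiotic | missing | missing |
| Azithromycin, no PAR, antibiotic Days 4–10 | 2 / 7 / 7 | unknown; 5 / 10 / 10 if all five doses taken |
| Azithromycin, no PAR, antibiotic Days 20–26 | 0 / 0 / 7 | unknown; 5 / 5 / 12 if all five doses taken |

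Rows 2 and 4 are zeros turned into missing. The last two rows are unknown values turned into counts that are 3 and 5 days short if all doses were taken.

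**3. Effect on rank.** Suppose subject A in the SAP example is the azithromycin subject of the last row and took all five doses. A's score falls from 1.05 to 1.00. A and B then tie at rank 1.5, D moves to 3 and C stays at 4. A goes from 2.5 to a share of the best rank because of an antibiotic taken two weeks after the visit.

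**4. The stop-date rule.** For a start on day *s* and a visit on day *e*, the completer rule gives *e* − *s* + 1 days (completion taken as Day 28). With mean course length *L*, the early-terminator rule gives min(*L*, *e* − *s* + 1). *L* is not in the documents; 5, 7 and 10 days are assumed.

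| Start | Completer rule, Day 5 / 11 / 28 | Mean rule, L = 5 | L = 7 | L = 10 |
|---|---|---|---|---|
| Day 1 | 5 / 11 / 28 | 5 / 5 / 5 | 5 / 7 / 7 | 5 / 10 / 10 |
| Day 3 | 3 / 9 / 26 | 3 / 5 / 5 | 3 / 7 / 7 | 3 / 9 / 10 |
| Day 8 | 0 / 4 / 21 | 0 / 4 / 5 | 0 / 4 / 7 | 0 / 4 / 10 |

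The excess at Day 28 is 11–16 days for a Day 8 start, 16–21 for Day 3 and 18–23 for Day 1. At Day 11 it is 0, 0–4 and 1–6. At Day 5 it is nil. If the Day 5 visit falls on Day 8, the largest excess in these cases is 8 − 5 = 3 (Day 1 start, L = 5).

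**5. Effect on an arm mean at Day 28.** With L = 7, one such record in an arm of 280 (the planned ATP-5 size; the ATP-28 size is not stated) adds (21 − 7)/280 = 0.05 day for a Day 8 start, or (26 − 7)/280 = 0.068 day for a Day 3 start. Ten Day 3 records would add 0.68 day.

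**The case against.** The strongest reply is that each fault needs conditions that may be uncommon. A placebo subject with a PAR is counted correctly. An azithromycin subject with no PAR and no other antibiotic is correctly missing. Compliance is assessed at the Day 5 visit, by interview if the memory aid is unavailable (Protocol 6.5, 7.3.2), so an observed Day 5 outcome with no dosing record should be rare. Where the OCO is missing, DOOR is missing anyway and the day count changes nothing. SAP 6.5.5 also relies on queries before lock to complete the medication records. All of this stands and limits the reach.

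Second, no antibiotic entry is not always a known zero. A subject lost early may have taken antibiotics that nobody recorded, and Table 11 counts study doses, not antibiotic days. This also stands, so a zero should be credited only where follow-up was obtained.

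Third, the SAP never states that study-drug days enter as zero without a PAR. That is an inference, but the SAP allows no other source for them and does not set the count to missing.

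Fourth, the correction makes missingness differ by arm. It does, because what is known differs by arm: placebo days do not depend on the PAR and azithromycin days do.

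A reader might infer that the stop-date rule inflates placebo use in particular, through more rescue antibiotics. The documents give no figure for missing stop dates by arm, so they do not support a direction.

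**Conclusion.** The concern holds in a limited form. With no PAR, the rule discards supportable zeros in placebo and confirmed never-dosed subjects, contrary to the placebo counting rule in the same section and out of line with Table 11. It also accepts an understated count for azithromycin subjects with unknown doses and any non-study antibiotic. In completers, an undated course can be overstated at Day 28 by 11–23 days under the assumed starts and course lengths.

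The wider reading, that the SAP miscounts known values generally, is not supported. Only the zeros are known values, and only with follow-up through the visit; the other two faults mishandle unknown ones.

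The first two faults affect the ITT DOOR analyses where the OCO is observed, and the bivariate analysis. They should not reach the antibiotic-day means in Tables 30 and 31, because ATP membership requires five doses. The stop-date fault mainly affects Table 31, where ATP-28 subjects have completed the Day 28 visit; it can also enter the exploratory tie-break in SAP 8.3.10.2. The primary endpoint does not use antibiotic days. The number of subjects affected is not given, so the net effect cannot be sized.

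**What to change.** Amend SAP 6.5.5 in three places.

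- **No PAR, placebo or confirmed never dosed:** count from the concomitant medication form, 0 if nothing is recorded, provided antibiotic follow-up was obtained through the visit in question; otherwise missing.
- **No PAR, azithromycin with unknown doses:** missing, whether or not a non-study antibiotic is recorded.
- **No stop date, study completer:** use the completion date only if the medication is recorded as ongoing, a status that Listing 15 already displays; otherwise apply the mean-course rule used for early terminators. The cap at the visit day is already in place.

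Reporting the number of affected records by arm would show whether any of this matters to the results. The cost is a few lines of SAP text and a small change to the derivation program, with no new data collection.
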